2.1.5.1 Adverse events variables

Adverse event observation period

- Pre-treatment adverse events are adverse events that developed or worsened or became serious from the signed informed consent date up to first administration of IMP.
- Treatment-emergent adverse events are adverse events that developed or worsened or became serious during the treatment-emergent adverse event period.
- Post-treatment adverse events are adverse events that developed or worsened or became serious during the post-treatment period.

All adverse events (including serious adverse events and adverse events of special interest (AESIs)) will be coded to a lower-level term (LLT), preferred term (PT), high-level term (HLT), high-level group term (HLGT), and associated primary system organ class (SOC) using the version of MedDRA currently in effect at Sanofi at the time of database lock.

Occurrence of adverse events (including Serious Adverse Events (SAEs) and Adverse Event of Special Interest (AESIs)) are recorded from the time of signed informed consent until the end of the study.

Adverse events of special interest (AESIs) include the following terms (their complete descriptions are provided in the protocol):

- Pregnancy of a female subject entered in a study as well as pregnancy occurring in a female partner of a male subject entered in a study with IMP, selected using the e-CRF “Pregnancy” tick box on the AE page.
- Symptomatic overdose (serious or non-serious) with IMP, selected using the e-CRF “symptomatic overdose of the IMP” tick box on the AE page.
- Alanine transferase (ALT) ≥ 3 ULN, selected using laboratory data.
- [REDACTED]
- Anaphylactic reactions or acute allergic reactions that require immediate treatment, selected using a CMQ coding list (see [Appendix J](#)).
- Severe injection site reactions, selected using HLT = “Injection site reaction” and an intensity equal to severe.
- Tuberculosis, selected using a CMQ coding list and/or Initiation of medications for suspected tuberculosis, selected using a WHO-DD CDG00737 “initiation of medications for suspected tuberculosis” (see [Appendix J](#)).
- Acute renal failure, selected using a CMQ coding list (see [Appendix J](#)) or using the e-CRF “Acute renal failure” tick box on the AE page.

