10.4.1.3 Adverse event of special interest

An AESI is an AE (serious or non-serious) of scientific and medical concern specific to the Sponsor's product or program, for which ongoing monitoring and immediate notification by the Investigator to the Sponsor is required. Such events may require further investigation in order to characterize and understand them. Adverse events of special interest may be added, modified or removed during a study by protocol amendment.

- Pregnancy of a female subject entered in a study as well as pregnancy occurring in a female partner of a male subject entered in a study with IMP.

Pregnancy occurring in a female patient entered in the clinical trial or in a female partner of a male patient entered in the clinical trial. It will be qualified as an SAE only if it fulfills one of the seriousness criteria (see [Section 10.4.1.2](#)).

- In the event of pregnancy in a female participant, IMP should be discontinued.
- Follow-up of the pregnancy in a female participant or in a female partner of a male participant is mandatory until the outcome has been determined.
- Symptomatic overdose (serious or non-serious) with IMP:
 - An overdose (accidental or intentional) with the IMP is an event suspected by the Investigator or spontaneously notified by the patient and defined as at least twice the intended dose given during a 4 day period.

Of note, asymptomatic overdose has to be reported as a standard AE.

- ALT > 3 x ULN: If increase in ALT >3 x ULN, see the "Increase in ALT" flow chart in [Appendix K](#) of the protocol.
 - However, if the increase in ALT is ≥ 2 x the baseline value (with baseline ALT \geq ULN) but ≤ 3 x ULN, then ALT should be re-tested within 72 hours of initial sample to determine if the retest value meets the AESI criterion of ALT > 3 x ULN. If so, proceed as above and follow the guidelines of [Appendix K](#). If not, monitoring of the laboratory findings will be up to the medical judgment of the Investigator.

- Other project specific AESI(s):
 - [REDACTED]

- Anaphylactic reactions or acute allergic reactions that require immediate treatment (refer to [Appendix I](#) for definition of Anaphylaxis)
- Severe injection site reactions (see [Appendix J](#))
- Tuberculosis or initiation of medications for suspected tuberculosis
- Acute renal failure (see [Appendix K](#)).

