2.4.5 Analyses of safety data

The summary of safety results will be presented by treatment group.

General common rules

All safety analyses will be performed on the safety population as defined in [Section 2.3.2](#), unless otherwise specified, using the following common rules:

- Safety data in patients who do not belong to the safety population (eg, exposed but not randomized) will be listed separately.
- The baseline value is defined as the last available value before the first administration of the IMP.
- The potentially clinically significant abnormality (PCSA) values are defined as abnormal values considered medically important by the Sponsor according to predefined criteria/thresholds based on literature review and defined by the Sponsor for clinical laboratory tests, vital signs, and ECG (PCSA version dated May 2014 [[Appendix A](#)]).

- PCSA criteria will determine which patients had at least 1 PCSA during the TEAE period, taking into account all evaluations performed during the TEAE period, including unscheduled or repeated evaluations. The number of all such patients will be the numerator for the treatment-emergent PCSA percentage.
- The treatment-emergent PCSA denominator by group for a given parameter will be based on the number of patients assessed for that given parameter in the TEAE period by treatment group on the safety population.
- For quantitative safety parameters based on central laboratory/reading measurements, descriptive statistics will be used to summarize results and change from baseline values by visit (baseline and post-baseline time points) and treatment group. Summaries will include the last and the worst on-treatment value. Only data sampled before or on the day of the last IMP administration will be included in the analysis. The worst on-treatment value is defined as the nadir and/or the peak post-baseline before or on the day of the last IMP administration according to the direction (minimum or maximum) of the abnormality as defined in the PCSA list.
- All measurements (scheduled or unscheduled) will be assigned to time points according to analysis windows as defined in [Section 2.5.4](#).
- The analysis of the safety variables will be essentially descriptive and no systematic testing is planned. Relative risks versus placebo and their 95% confidence intervals may be provided, if relevant.

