- All TEAEs regardless of relationship and related to IMP by primary SOC, HLGT, HLT and PT, showing the number (%) of patients with at least 1 TEAE, sorted by the internationally agreed SOC order. The other levels (HLGT, HLT, PT) will be presented in alphabetical order.
- All TEAEs by maximal severity, presented by primary SOC and PT, showing the number (%) of patients with at least 1 TEAE by maximal severity (ie, mild, moderate, or severe), sorted by the sorting order defined above.

Analysis of all treatment emergent SAEs

- All treatment-emergent SAEs by primary SOC, HLGT, HLT, and PT, showing the number (%) of patients with at least 1 serious TEAE, sorted by the internationally agreed SOC order. The other levels (HLGT, HLT, PT) will be presented in alphabetical order.
- All treatment-emergent SAEs by primary SOC and PT, showing the number (%) of patients with at least 1 serious TEAE, sorted by the sorting order defined above.
- All treatment-emergent SAEs regardless of relationship and related to IMP, by primary SOC, HLGT, HLT, and PT, showing the number (%) of patients with at least 1 treatment-emergent SAE, sorted by the internationally agreed SOC order. The other levels (HLGT, HLT, PT) will be presented in alphabetical order.
- Listings will be provided for all SAEs by treatment arm during the TEAE period.

Analysis of all TEAEs leading to treatment discontinuation

- All TEAEs leading to treatment discontinuation, by primary SOC, HLT, HLT, and PT, showing the number (%) of patients sorted by the internationally agreed SOC order. The other levels (HLGT, HLT, PT) will be presented in alphabetical order.
- All TEAEs leading to treatment discontinuation, by primary SOC and PT, showing the number (%) of patients with at least 1 TEAE, sorted by the internationally agreed SOC order and by decreasing incidence of PTs within each SOC.
- Listing will be provided for all TEAE leading to permanent treatment discontinuation by treatment arm.

Analysis of treatment-emergent AESIs

All treatment-emergent AESIs, by AESI category and PT, showing the number (%) of patients by treatment group, sorted by decreasing incidence of PT within each AESI category. The AESIs categories and details of the MedDRA coding are provided in [Section 2.1.5.1](#).

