Appendix A Potentially clinically significant abnormalities criteria

CRITERIA for POTENTIALLY CLINICALLY SIGNIFICANT ABNORMALITIES for Phase 2/3 studies (oncology excepted)

Parameter	PCSA	Comments
Clinical Chemistry		
ALT	By distribution analysis: >3 ULN >5 ULN >10 ULN >20 ULN	Enzymes activities must be expressed in ULN, not in IU/L. Concept paper on DILI - FDA draft Guidance Oct 2007. Internal DILI WG Oct 2008. Categories are cumulative. First row is mandatory. Rows following one mentioning zero can be deleted.
AST	By distribution analysis: >3 ULN >5 ULN >10 ULN >20 ULN	Enzymes activities must be expressed in ULN, not in IU/L. Concept paper on DILI - FDA draft Guidance Oct 2007. Internal DILI WG Oct 2008. Categories are cumulative. First row is mandatory. Rows following one mentioning zero can be deleted.
Alkaline Phosphatase	>1.5 ULN	Enzymes activities must be expressed in ULN, not in IU/L. Concept paper on DILI - FDA draft Guidance Oct 2007. Internal DILI WG Oct 2008.
Total Bilirubin	>1.5 ULN >2 ULN	Must be expressed in ULN, not in μ mol/L or mg/L. Categories are cumulative. Concept paper on DILI - FDA draft Guidance Oct 2007. Internal DILI WG Oct 2008.
Conjugated Bilirubin	>35% Total Bilirubin and TBILI>1.5 ULN	Conjugated bilirubin dosed on a case-by-case basis.
ALT and Total Bilirubin	ALT >3 ULN and TBILI >2 ULN	Concept paper on DILI - FDA draft Guidance Oct 2007. Internal DILI WG Oct 2008. To be counted within a same treatment phase, whatever the interval between measurement.

**CRITERIA for POTENTIALLY CLINICALLY SIGNIFICANT ABNORMALITIES
for Phase 2/3 studies (oncology excepted)**

Parameter	PCSA	Comments
CPK	>3 ULN >10 ULN	FDA Feb 2005. Am J Cardiol April 2006. Categories are cumulative. First row is mandatory. Rows following one mentioning zero can be deleted.
CLcr (mL/min) (Estimated creatinine clearance based on the Cokcroft-Gault equation)	<15 (end stage renal disease) ≥15 - <30 (severe decrease in GFR) ≥30 - <60 (moderate decrease in GFR) ≥60 - <90 (mild decrease in GFR) ≥90 (normal GFR)	FDA draft Guidance 2010. Pharmacokinetics in patients with impaired renal function-study design, data analysis, and impact on dosing and labeling.

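### The SAP sets the ALT adverse event of special interest at 3 x ULN or more, but the protocol definition it cites and its own Appendix A require more than 3 x ULN

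*SAP*

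**What the plan says.** SAP 2.1.5.1 introduces its list this way: "Adverse events of special interest (AESIs) include the following terms (their complete descriptions are provided in the protocol". The ALT entry in that list is "Alanine transferase (ALT) ≥ 3 ULN, selected using laboratory data". SAP 2.4.5.1, which specifies the table of treatment-emergent AESIs, points back to the same place: "The AESIs categories and details of the MedDRA coding are provided in [Section 2.1.5.1".

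Protocol 10.4.1.3 gives the AESI as "ALT > 3 x ULN: If increase in ALT >3 x ULN", and Table 3 in Protocol 10.4.6 repeats the strict limit. Protocol 10.4.1.3 also covers a rise to at least twice a baseline value that was itself at or above ULN, where the new value stays within the AESI limit. The instruction for that case is "then ALT should be re-tested within 72 hours of initial sample to determine if the retest value meets the AESI criterion of ALT > 3" (the multiple is again of the ULN). A value of exactly 3 x ULN is therefore on the non-AESI side in the protocol.

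For ALT as a PCSA, SAP Appendix A gives "By distribution analysis: >3 ULN >5 ULN >10 ULN >20 ULN". Its combined ALT and bilirubin criterion also uses ALT above 3 x ULN. The PCSA tables cover the same period as the treatment-emergent AESI table: "PCSA criteria will determine which patients had at least 1 PCSA during the TEAE period".

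**The concern.** Pregnancy and symptomatic overdose are identified from tick boxes on the case report form. The ALT AESI is instead derived from laboratory values, so the inequality written in SAP 2.1.5.1 decides who is selected. Because the AESI table refers back to that section, the line works as a programming specification.

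The SAP thus cites a definition and then states a different one. A patient could appear in the AESI output for ALT who met neither the protocol's AESI criterion nor the SAP's own PCSA criterion. At stake is a small, unexplained discrepancy between two safety outputs built on the same ALT data, and between the AESI output and what the protocol asked sites to report.

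**Working it through.** The plan states no figure to reproduce here. The check compares the texts and then asks which values the two rules classify differently.

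**1. The limit in each place**

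| Place | Purpose | Limit | ALT exactly 3 x ULN |
|---|---|---|---|
| SAP 2.1.5.1 | AESI for analysis, from laboratory data | ≥ 3 x ULN | counted |
| Protocol 10.4.1.3 | AESI definition | > 3 x ULN | not an AESI |
| Protocol Table 3 (10.4.6) | AESI reporting | > 3 x ULN | not an AESI |
| SAP Appendix A | lowest ALT PCSA category | > 3 x ULN | not a PCSA |

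Three of the four are strict. SAP 1.6 lists the modifications made in this SAP version, and the ALT limit is not among them.

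**2. Which values differ**

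Values with ALT ≥ 3 x ULN, less those with ALT > 3 x ULN, leave only ALT = 3 x ULN. A patient with any higher value in the treatment-emergent period qualifies under both rules. So a patient is classified differently only if the peak in that period is exactly 3.0 x ULN.

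The documents give neither the ALT ULN nor the reporting precision. Assuming whole-number results, the single discordant value would be:
- ULN 30: 3 x 30 = 90
- ULN 40: 3 x 40 = 120
- ULN 55: 3 x 55 = 165

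**3. Direction**

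Every patient above 3 x ULN is also at or above it. Through this symbol the SAP count can exceed the protocol or PCSA count, and it cannot fall below either.

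**4. Size of one such patient**

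With the planned 47 per arm, all treated and analysed:
- one arm: 1/47 = 2.13%, about 2.1 percentage points of the ALT AESI row
- both arms: 1/94 = 1.06%, about 1.1 percentage points

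The arm's overall AESI rate moves only if that patient has no other AESI.

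**5. After the change**

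With > 3 x ULN in SAP 2.1.5.1, no ALT value is classified differently by the protocol AESI, the SAP AESI and the lowest PCSA category.

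**The case against.** The case for leaving this alone has four parts.

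- **The SAP already refers to the protocol for full descriptions.** A programmer who followed the reference would find the strict limit. That softens the problem, but the explicit symbol in the SAP still contradicts the text it cites, and the AESI table is directed to the SAP line.
- **A boundary patient may never reach the table.** SAP 2.4.5.1 presents AESIs by category and preferred term, with a listing of intensity, seriousness and relationship. Protocol 10.4.3 records a laboratory abnormality as an adverse event only under listed conditions, one of which is being an AESI. A value of exactly 3 x ULN with no adverse event record has no preferred term. Selection from laboratory data points the other way, so the documents leave the outcome open. This stands, and it is why the point says only that such a patient could be counted.
- **AESI and PCSA percentages can differ anyway.** SAP 2.4.5.1 divides adverse event counts by the safety population. SAP 2.4.5 divides PCSA counts by the patients assessed for the parameter. This stands: aligning the symbol aligns the cut-off, but it does not guarantee equal percentages.
- **Few patients, if any, will sit exactly on the limit**, and the safety analysis is descriptive. This stands too.

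A reader might infer more: that a boundary patient certainly has no AESI report or form because sites act only above 3 x ULN. The documents do not support that. Protocol 10.4.1.3 requires a retest for some values at or below the limit, and a retest above it becomes a reportable AESI. The ALT flow chart in Appendix K is not legible in the text available, so its thresholds cannot be checked.

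A reader might also widen the affected range by supposing that ratios are rounded before classification. No rounding rule is given, so that is not claimed.

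**Conclusion.** The inconsistency is real and the SAP line is wrong as written, because it contradicts both the protocol definition it relies on and the SAP's own Appendix A. It is minor. It affects only a patient whose peak ALT in the treatment-emergent period is exactly 3.0 x ULN, probably none or very few of about 94.

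The figure of about 2.1 points applies to the ALT AESI row of one arm. It assumes that such a patient exists, that the arm has 47 patients in the safety population, and that the laboratory-based selection places the patient in the table. No probability of this can be given from the documents. Efficacy results are unaffected.

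The point concerns the analysis definition only. It takes no view on what ALT level should trigger reporting or patient management.

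**What to change.** In SAP 2.1.5.1, change the ALT AESI from ≥ 3 ULN to > 3 ULN, so that it matches Protocol 10.4.1.3, Table 3 and SAP Appendix A. If the inclusive limit is intended, list it in SAP 1.6 as a deliberate departure and note it under the AESI table.

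The cost is one symbol, or one sentence, plus the matching line in the programming specification. No data collection, protocol text or site procedure changes.

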10.4 OBLIGATION OF THE INVESTIGATOR REGARDING SAFETY REPORTING

10.4.1 Definitions of adverse events

10.4.1.1 Adverse event

An AE is any untoward medical occurrence in a patient or clinical investigation patient administered a pharmaceutical product and which does not necessarily have to have a causal relationship with this treatment.

Intensity of an AE is defined as:

- Mild: no modification of daily activities and does not require mandatory corrective/symptomatic treatment
- Moderate: hinders normal daily activities and/or requires mandatory corrective/symptomatic treatment
- Severe: prevents daily activities and requires mandatory corrective/symptomatic treatment

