Appendix J Assessment of Local Injection Site Reactions

Reaction to Injectable Product	Mild (Grade 1)	Moderate (Grade 2)	Severe (Grade 3)	Very Severe (Grade 4)
Pain	Does not interfere with activity	Interferes with activity or repeated use of non-narcotic pain reliever	Prevents daily activity or repeated use of narcotic pain reliever	Emergency Room (ER) visit or hospitalization
Tenderness	Mild pain to touch	Pain with movement	Significant pain at rest	ER visit or hospitalization
Erythema / Redness *	2.5 – 5 cm	5.1 – 10 cm	>10 cm	Necrosis or exfoliative dermatitis
Swelling **	2.5 – 5 cm and does not interfere with activity	5.1 – 10 cm or interferes with activity	> 10 cm or prevents daily activity	Necrosis
Itching	Does not interfere with activity	Interferes with activity or repeated use of topical or systemic treatment	Prevents daily activity or leads to other significant dermatologic conditions (such as infection, scarring, etc.)	ER visit or hospitalization
Other (Please specify)***	No modification of daily activities and/or does not require symptomatic treatment.	Hinders normal daily activities and/or requires symptomatic treatment.	Prevents daily activities and requires symptomatic treatment.	ER visit or hospitalization

* In addition to grading the measured local reaction at the greatest single diameter, the measurement should be recorded as a continuous variable.

[figure not shown]
** Swelling should be evaluated and graded using the functional scale as well as the actual measurement.

*** Please specify the other signs or symptoms (for example, hematoma, discoloration, re-activation, etc).

ADAPTED from the toxicity grading scale table from the FDA Draft Guidance for Industry: Toxicity Grading Scale for Healthy Adult and Adolescent Volunteers Enrolled in Preventive Vaccine Clinical Trials April 2005

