Appendix J Codelists for background therapy definitions, AESIs and related hepatic disorder

Requested list	Type (cmq, smq, others)	Name or Code (cmqname, smqcd, others)	Description (cmqdesc or SMQ_ShortName, others)	Scope (smq) / prim_sec (soc)
Reqlist	Type	Codename	Desc	Scope
Background therapy definition 2	CDG	CDG00103	METHOTREXATE_mono_and_multiingredients	
Background therapy definition 2	CDG	CDG20046	MYCOPHENOLATE_MOFETIL_mono_and_multi_ingredients	
Background therapy definition 2	CDG	CDG00039	AZATHIOPRINE_mono_and_multi_ingredients	
Background therapy definition 2	CDG	CDG20011	CICLOSPORIN_mono_and_multi_ingredients	
Background therapy definition 2	CDG	CDG00040	CYCLOPHOSPHAMIDE_mono_and_multi_ingredients	
Background therapy definition 1	CDG	CDG00014	ANTINEOPLASTIC AND IMMUNOMODULATING AGENTS	
Background therapy definition 1	CDG	CDG10109	SYSTEMIC HORMONAL PREPARATIONS, EXCL. SEX HORMONES AND INSULINS	
Acute renal failure	SMQ	Acute renal failure (SMQ)	Acute renal failure Narrow	Narrow
Tuberculosis	CMQ	GLB_TUBERCULOSIS	Tuberculosis	
Anaphylactic reactions or acute allergic reactions that require immediate treatment	CMQ	Anaphylactic reaction Narrow	Anaphylactic reaction Narrow	
Hepatic disorder	SMQ	Hepatic disorders (SMQ)	Hepatic disorders Narrow	Narrow

Signature Page for VV-CLIN-0196174 v2.0
act14604-16-1-9-sap

Approve & eSign	[REDACTED]
	07-Mar-2019 16:13:03 GMT+0000

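### The SAP selects severe injection-site reaction AESIs by AE intensity, but the protocol defines them by its Appendix J grades, so qualifying events can be left out of the AESI table

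*SAP*

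**What the plan says.** **Injection-site reactions.** Protocol 10.4.1.3 lists among the AESIs "Severe injection site reactions (see" Appendix J of the protocol). That appendix grades six components (pain, tenderness, erythema, swelling, itching, other) from 1 to 4, with Grade 3 headed severe and Grade 4 very severe. Protocol 10.6.2.1 has the site report one AE term for a non-allergic local reaction and describe its components on a dedicated e-CRF screen.

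SAP 2.1.5.1 selects this AESI by the injection-site high-level term "and an intensity equal to severe". It refers neither to the Appendix J grades nor to that screen. The intensity scale is defined in protocol 10.4.1.1: "Severe: prevents daily activities and requires mandatory corrective/symptomatic treatment". SAP 2.4.5.1 confirms that it has three levels, tabulating TEAEs by "maximal severity (ie, mild, moderate, or severe").

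**Allergic reactions.** The AESI category in both documents has two parts: "Anaphylactic reactions or acute allergic reactions that require immediate treatment". SAP 2.1.5.1 selects it by a customized query only, and SAP Appendix J gives one list for the whole category, named Anaphylactic reaction Narrow.

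**The concern.** The definition that obliges a site to report an AESI and the rule that decides whether it is counted as one rest on different scales. Protocol Table 3 requires severe injection-site reactions to be reported within 24 hours. If the counting rule is narrower than the reporting rule, an event can be reported to the sponsor as an AESI and then be absent from the AESI table and listing planned in SAP 2.4.5.1. For a weekly subcutaneous antibody, local tolerability is one of the safety results a reader will look for. The protocol synopsis names graded severity and diameter of local reactions as safety endpoints, and the SAP's safety sections describe no separate table of the Appendix J grades. The AESI table is therefore the main place where the worst local reactions would be identified as such.

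**Working it through.** The documents give no figure to reproduce, so the check compares definitions.

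**Step 1: the intensity rule.** Under protocol 10.4.1.1, severe requires two conditions together: daily activities prevented, and mandatory corrective or symptomatic treatment. There is no size criterion. Activities hindered and/or mandatory treatment needed is moderate. Neither is mild.

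**Step 2: each Grade 3 row of protocol Appendix J against that rule.**

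| Component | What is enough for Grade 3 | Can be met without severe intensity? |
|---|---|---|
| Pain | "Prevents daily activity or repeated use of narcotic pain reliever" | Yes: narcotic use alone |
| Tenderness | Significant resting pain | Yes: no activity or treatment condition |
| Erythema | Diameter over 10 cm | Yes: size alone |
| Swelling | "> 10 cm or prevents daily activity" | Yes: size alone |
| Itching | Activity prevented, or another significant skin condition results | Yes: the skin condition alone |
| Other | Activity prevented and symptomatic treatment required | No: essentially the same wording |

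Five of the six rows can be met without severe intensity; 6 − 5 = 1 row matches.

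**Step 3: what literal use of the two scales gives.** Erythema over 10 cm with activities unchanged and no mandatory treatment is Grade 3 in Appendix J but mild in 10.4.1.1. Pain needing repeated narcotics, with activities hindered but not prevented, is Grade 3 but moderate. The SAP filter would drop both.

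**Step 4: Grade 4.** Appendix J has four levels and AE intensity has three, so Grade 4 has no level of its own. Four of the six Grade 4 rows (pain, tenderness, itching, other) rest on an emergency-room visit or hospitalization. The erythema and swelling rows rest on necrosis or, for erythema, exfoliative dermatitis. None of these conditions is part of the intensity definition. I assume that an AESI for severe reactions includes the very severe grade.

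**Step 5: the allergic category.** Protocol 10.6.3.1 treats anaphylaxis as possibly the most severe form of allergic reaction, so acute allergic reaction is the wider concept. Protocol 11.4.3.1 names hypersensitivity separately from anaphylaxis among the AESI categories and leaves the complete list to the SAP. The legible SAP text names no hypersensitivity list. Of the two parts of the definition, one (anaphylaxis) has a list named for it. For acute renal failure, by contrast, the SAP already accepts either a code list or an e-CRF tick box.

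**The case against.** Four points on the other side have weight.

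1. **Investigators assign intensity.** Appendix J heads its columns mild, moderate, severe and very severe, and nothing forbids a site from entering that grade in the intensity field. A reader might infer that every size-only Grade 3 reaction is lost. The documents do not support that; they support only that such events can be lost.
2. **The events stay visible elsewhere.** All TEAEs are tabulated, including by maximal severity. Severe local reactions per Appendix J are also a permanent-discontinuation criterion (protocol 10.3.3), and SAP 2.4.5.1 tabulates and lists TEAEs leading to discontinuation. Inpatient hospitalization would make an event serious. A reader might infer that the study report would lose these events; in fact the effect is on their classification in the AESI table and listing. Safety analysis is essentially descriptive, so no test is affected.
3. **Not every form entry is an AE.** Protocol 10.6.3.1 sends transient irritant reactions needing no intervention to the complementary form only. Some size-only reactions may therefore never be AEs, and selecting on the form alone would bring in records without a preferred term.
4. **The query's contents are unknown.** It is a customized query assigned to the full two-part category. A reader might infer from its name that it covers anaphylaxis only, but its terms are not in the documents.

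SAP 2.1.5.1 also says that complete AESI descriptions are in the protocol. That confirms which definition governs but does not alter the selection rule. Points 1 to 3 limit the consequence and shape the fix, and point 4 reduces the allergic part to a question. None removes the mismatch between the scales.

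**Conclusion.** The injection-site point holds. The SAP's stated rule is narrower than the protocol definition in five of six Grade 3 rows and has no level for Grade 4, so qualifying AEs can be missing from the AESI table and listing. How many depends on how sites fill in the intensity field, which the documents do not say; no count can be derived. If every site entered the Appendix J grade as intensity, with Grade 4 entered as severe, nothing would be lost. If every site applied 10.4.1.1 literally, reactions of the kind in step 3 that are reported as AEs would drop out.

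The allergic point is an open question: the list's name and the absence of a hypersensitivity list give reason to ask, but do not show a gap.

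**What to change.** In SAP 2.1.5.1, define the injection-site AESI as an AE under the injection-site high-level term with **either** any component graded 3 or 4 per protocol Appendix J on the local injection site reaction e-CRF screen, **or** AE intensity of severe. Limit it to reactions reported as AEs, so that form-only irritant reactions stay out.

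For the allergic category, state the terms in the query and confirm that they cover non-anaphylactic acute allergic reactions. If they do not, add a hypersensitivity list, or add AEs that have a General Allergic Reaction complementary form and recorded corrective treatment. Protocol 10.4.3 has corrective treatment recorded, but the documents do not show that its immediacy is captured, so this second route would only approximate the protocol criterion.

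The cost is a change of SAP wording and a little extra programming to link the form to the AE record. The form layouts are not in the documents, so check first that component grades are held as analyzable fields. AESI counts may rise slightly. No data collection or clinical rule changes.
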